The Effect of Baduanjin on Physical Fitness and Bone Density in Maintenance Hemodialysis Patients

Affiliated Hospital of Nantong University

2023-07-10

The Effect of Baduanjin on Physical Fitness and Bone Density in Maintenance Hemodialysis Patients

1. Research Background

Chronic kidney disease bone mineral metabolism disorders exist in maintenance dialysis (MHD) patients, with a high incidence of bone and joint pain of 58.7%. At the same time, the motor ability of patients with chronic kidney disease decreases as the disease progresses, and MHD patients gradually experience muscle atrophy, decreased upper limb motor ability, slow walking, and slow sitting and standing. Long term lack of exercise further exacerbates bone and joint lesions. Functional fitness refers to the comprehensive physiological functions of the body's cardiopulmonary, skeletal muscle system and the quality of softness and balance, and is now mainly targeted at the elderly and the frail; it evaluates the level of daily life activities, reflects the decline of body functions, and is an important indicator of health.

Studies have shown that exercise can improve joint function, alleviate joint pain, increase muscle strength, and improve inflammation in MHD patients. However, due to the lack of relevant evidence-based evidence, exercise rehabilitation has not yet been included in routine clinical care plans. Clinical research data on rehabilitation exercises for MHD patients are needed to recommend reasonable, feasible and acceptable exercise modalities for the national population. Baduanjin is an ancient health art that combines breathing and exhaling with physical exercise, and it is a multifactorial intervention that integrates physical, mental, emotional, spiritual and behavioral elements, with moderate exercise volume, which belongs to the category of aerobic exercise. Although studies have suggested that Baduanjin has a good therapeutic effect on people with physical fitness disorders, and clinical studies on the prevention of bone loss and the improvement of bone mineral density have also been conducted gradually. However, there is still a lack of information on the application of Baduanjin in MHD patients. However, there is still a lack of information on the application of Baduanjin in MHD patients.

2.1 Research Purpose

Main objective: To observe the effect of Baduanjin on physical fitness and bone density of maintenance dialysis patients.

Secondary objective: To observe the effect of Baduanjin on the quality of life and emotions of MHD patients.

2.2 Study Description

The aim of this study is to observe the therapeutic effect of Baduanjin on improving physical fitness and bone density in MHD patients. A total of 50 MHD patients will be included and randomized into an intervention group of 25 cases and a control group of 25 cases. The intervention group undergo a 30 minute Baduanjin exercise under the guidance of a professional doctor before the dialysis day, including a 5-minute warm-up exercise, a 20 minute Baduanjin exercise, and a 5-minute relaxation exercise. The intervention group practice three days a week, while the control group maintain routine treatment and daily activities. Measure the indicators of each group at baseline, months 6, 12. The evaluation of physical fitness is based on the scores (which include muscle strength measurement; five-times sit-to-stand test; timed "up and go" test; sitting forward flexion test; standing on one-leg with eyes closed test). The bone mineral density test is based on the result of the double-energy DXA line. The quality of life score is based on the SF-36 score, and the emotional

score is based on the anxiety and depression scale.

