2.3 Grouping Criteria

Inclusion Criteria:

- Age > 18 years old, ≤ 75 years old
- Having received MHD treatment in this dialysis center for more than 3 months and maintaining stable condition
- Having normal comprehension ability, clear verbal expression, informed consent and willingness to participate in this study
- Having free movement ability, and being able to tolerate Baduanjin exercise after cardiopulmonary exercise test
- Right-handed, with fistula in the non-dominant hand

Exclusion Criteria:

- Patients who usually practice traditional Chinese medicine exercises such as tai chi;
- Patients who are recently complicated with severe infections, active malignant tumors, severe cardiopulmonary insufficiency, gastrointestinal bleeding, nervous system diseases and cannot tolerate exercise;
- Patients with various orthopedic, neurological, and other diseases that cause muscle and joint deformities that affect grip strength measurement;
- Patients with senile dementia, hearing impairment, comprehension abnormalities, mental disorders, unclear verbal expression or unwilling to participate in this study;
- Patients with hemoglobin < 70g/L, carbon dioxide binding capacity < 13mmol/L, and blood potassium > 6.5mmol/L in laboratory tests and no significant improvement after treatment;
- Patients who are participating in other clinical studies.

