2.4 Outcome Measures

Primary Outcome Measure:

1) Muscle strength measurement

Grip strength can reflect the strength of hand muscles. The grip strength of both hands of patients was measured using a domestic gripper. The patient took an upright position and grasped the handle with the maximum force. When the display on the machine stopped changing, the value was recorded. The test was repeated three times, and the maximum value was taken to record the results.

2) Five-times Sit-to-Stand Test (FTSST)

The five-times sit-to-stand test is used to evaluate the functional strength of the lower

limbs. MHD patients sat on a 46cm chair without armrests, with their feet on the ground and their backs not resting on the chair. Their hands were crossed on their shoulders. They stood up from the chair as quickly as possible without arm support. They completed five sitting and standing movements, and the completion time was recorded. During the test, the patient kept his hands crossed and his knees completely straightened. Three tests were completed, with a one-minute rest between tests. The average value of the three tests was statistically analyzed.

3) Timed "up and go" test (TUGT)

The timed "up and go" test is often used to evaluate functional mobility such as balance and walking required in daily life. MHD patients were seated in a back chair with armrests (the seat was about 46cm high, and the armrest was about 21cm high). A guide line was placed on the ground 3m away from the chair. After the test began, the patient left the chair, stood firmly and walked forward for 3m as fast as possible, crossed the guide line, turned around, and returned to the chair to sit down. The walking aids were not allowed during the test. The test was conducted 3 times in total, with a 1-minute rest between adjacent tests. The average value of the 3 tests was taken for statistical analysis.

4) The sitting forward flexion test

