2.5 Statistical analysis, confidentiality plan

In terms of statistical analysis, SPSS 27.0 statistical software is used to establish a database and perform statistical processing. Descriptive statistical analysis, qualitative indicators are described as percentages, and quantitative indicators are described as mean \pm standard deviation. The data is subjected to normality testing and corresponding testing methods are adopted based on whether it follows a normal distribution. Qualitative data comparison adopts chi square test. Quantitative data conforms to normal distribution, t-test is used for comparison between two groups, and nonparametric test is used for abnormal distribution and $P < 0.05$ is considered statistically significant.

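### The planned between-group test in section 2.5 uses neither the measured baseline value nor sex or age, so it gives up precision and leaves a chance sex imbalance uncorrected if follow-up values are compared

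*Combined protocol and SAP*

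**What the plan says.** - **Allocation (2.2).** Fifty patients are to be "randomized into an intervention group of 25 cases and a control group of 25 cases". No randomisation method, blocking or stratification factor is described.
- **Visits (2.2).** "Measure the indicators of each group at baseline, months 6, 12". A baseline value of every primary outcome should therefore be available.
- **Eligibility (2.3).** "Age > 18 years old, ≤ 75 years old". No criterion restricts sex, so both sexes are eligible by implication. No expected sex mix is given.
- **Outcomes (2.4).** Grip strength is the first primary measure: "The test was repeated three times, and the maximum value was taken to record the results". It is a raw value, not standardised for sex, age or body size. Bone mineral density is likewise in raw units (g/cm²). The wording about change is attached only to the secondary scales (SF-36 with EQ-5D-5L, and HADS). For the primary measures the plan does not say whether follow-up values or changes are compared.
- **Analysis (2.5).** For normally distributed quantitative data a "t-test is used for comparison between two groups"; otherwise a nonparametric test. No covariate of any kind is named.

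**The concern.** Raw grip strength varies widely between patients, and part of that spread is likely to come from sex. A two-sample test on follow-up values leaves all of it in the error term. With 25 per arm and no power calculation in the plan, precision is scarce: a difference of about 0.81 SD is needed for 80% power at a two-sided 5% level.

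Unrestricted allocation can also leave one arm with several more men than the other. The reported difference then mixes the effect of Baduanjin with the sex difference, and nothing in the stated test separates them. The information needed to remove most of this spread is already being collected at baseline, but section 2.5 does not use it.

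**Working it through.** **Inputs from the documents.** 50 patients, 25 per arm; raw grip value; two-sample test without covariates; baseline measured.

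**Inputs assumed, because the documents give none.** 30 men of 50 (60%); male-female grip gap D of 8-12 kg, centre 10; within-sex SD s = 6.5 kg; within-sex baseline to follow-up correlation r = 0.8, with 0.6 as a check; two-sided 5% level. There is no stated effect size, SD or power, so the sample size of 50 cannot be reproduced.

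**1. How unequal the arms become.** The number of men in one arm is hypergeometric (25 drawn from 50, of whom 30 are men).
- Variance = 25 × 0.6 × 0.4 × 25/49 = 3.06, so SD = 1.75 men.
- The between-arm difference in men has SD 2 × 1.75 = 3.50, which is 3.50/25 = 0.14 as a proportion.
- P(difference of at least 4 men) = 38.7%; P(at least 6) = 14.8%; P(at least 8) = 4.2%.
- With 28 men, P(at least 6) = 15.4%. With 25 or 35 men the difference must be odd: P(at least 5) = 25.8% or 21.7%, and P(at least 7) = 8.9% or 6.2%.

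**2. What that does to a comparison of follow-up grip.** Shift = D × difference in male proportion.

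| Gap D | 1-SD shift (0.14 × D) | Shift at 6 men (D × 6/25) |
|---|---|---|
| 8 kg | 1.1 kg | 1.9 kg |
| 10 kg | 1.4 kg | 2.4 kg |
| 12 kg | 1.7 kg | 2.9 kg |

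**3. Standard error of the group difference** (D = 10, s = 6.5, r = 0.8). The factor for 25 per arm is √(2/25) = 0.283.
- Unadjusted: total variance = 6.5² + 0.6 × 0.4 × 10² = 42.25 + 24 = 66.25; SD 8.14; SE = 8.14 × 0.283 = 2.30 kg.
- Sex in the model: SE = 6.5 × 0.283 = 1.84 kg.
- Baseline in the model: overall correlation = (0.8 × 42.25 + 24)/66.25 = 0.872; SE = 2.30 × √(1 − 0.872²) = 1.13 kg.
- Baseline and sex: SE = 1.84 × √(1 − 0.8²) = 1.10 kg.
- Change score without covariates: SE = 6.5 × √(2 × 0.2) × 0.283 = 1.16 kg.

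Simulation under unrestricted allocation, which also counts the small cost of estimating the covariates, gives about 2.30, 1.87, 1.14 and 1.13 kg for the first four.

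At r = 0.6 the overall correlation is (0.6 × 42.25 + 24)/66.25 = 0.745. The formulas give 2.30 × √(1 − 0.745²) = 1.54 kg with baseline and 1.84 × 0.8 = 1.47 kg with baseline and sex. Baseline still does more than sex alone.

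**4. Detectable difference at 80% power** (0.8087 SD, noncentral t).
- Unadjusted: 0.8087 × 8.14 = 6.58 kg.
- Sex removed: 0.8087 × 6.5 = 5.26 kg.
- Baseline removed: residual SD 8.14 × √(1 − 0.872²) = 3.98 kg; 0.8087 × 3.98 = 3.2 kg.

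**5. Validity.** In simulation (28 men, D = 10, s = 7), the unadjusted t-test rejects in 5.0% of trials with no effect, and its mean estimate is about zero. Restricted to allocations where the intervention arm's male share is at least 20 points higher, the unadjusted estimate is off by about 2.7 kg, the sex-adjusted and change-score estimates by about 0, and baseline ANCOVA without sex by 0.4 kg (r = 0.8) to 0.8 kg (r = 0.6). That remainder is the reason to keep sex in the model next to baseline.

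**The case against.** **The test is not biased.** A reader might infer that an unstratified, unadjusted trial of this size produces false effects. It does not: its standard error already contains the between-sex variance, and type I error stays at 5%. This stands. The point is lost precision, and an uncorrected shift in the minority of allocations that are badly unbalanced.

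**A shift of 2-3 kg is not the expected case.** A reader might also take that as what will happen. No sex mix, sex gap or SD is in the documents. Under the assumptions here such a shift needs roughly 6 or more extra men in one arm, about one allocation in seven. At an 8 kg gap a shift of 2 kg or more occurs in only 4%. This stands too, which is why the typical 1.1-1.7 kg is given first.

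**The shift depends on what is compared.** A change-score comparison would cancel a constant sex gap and, at r = 0.8, nearly match ANCOVA. This stands as a condition. Section 2.5 does not commit to change scores for the primary outcomes, so it does not remove the concern.

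**Missing stratification is not itself a fault.** Once baseline is modelled, stratifying by sex with sex in the model moves the simulated standard error only from 1.13 to 1.12 kg (gap 10), or from 1.07 to 1.03 kg (gap 12, within-sex SD 6). This stands; stratification is close to a preference.

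**Only grip is quantified.** It is one of six primary measures. No figure is offered for bone density or for age, and the kilogram results should not be carried over to them.

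**Conclusion.** The concern holds as one about analysis. Section 2.5 leaves out a baseline value that the trial measures, together with sex and age, although eligibility is broad and outcomes are in raw units. Against a comparison of follow-up grip values, and under the stated assumptions, baseline adjustment about halves the standard error (2.3 to 1.1 kg); sex alone takes it to about 1.9 kg. The chance sex imbalance is secondary: typically 1.1-1.7 kg for gaps of 8-12 kg, and at least 1.9-2.9 kg in about 15% of allocations.

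All of these sizes rest on an assumed 60% men, the assumed gap and SD, and the assumed correlation. That no covariate is specified does not rest on any assumption. The documents do not support a claim of bias, of inflated type I error, or that unstratified randomisation invalidates the trial.

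**What to change.** **In 2.5**, for each quantitative primary outcome, replace the two-sample test with ANCOVA of the follow-up value on group, baseline value, sex and age, and report the adjusted difference with its confidence interval. State in advance that a rank-based or transformed version will be used if residuals are clearly non-normal, so that the present nonparametric branch has a counterpart. This also settles whether follow-up values or changes are compared.

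**In 2.2, optionally**, stratify the randomisation by sex with concealed permuted blocks, keeping sex in the model to match.

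**Cost.** Three degrees of freedom and a few more terms in SPSS; no extra patients, visits or measurements. If stratified: two lists instead of one, a possible slight departure from 25/25 when blocks are unfinished, and some predictability of the next assignment with small blocks, since an exercise arm is hard to conceal from staff.

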The sitting forward flexion test is often used to evaluate the flexibility of the lower limbs of patients. The patient straightened the knee joint, sat on the flat ground with both feet flat on the test board, bent forward, straightened both arms forward, and gradually pushed the cursor with both middle fingertips to the farthest possible distance. The measuring device was 0 point along the plane of the foot pedal board, negative inward, positive forward, in centimeters. The knee joint could not be bent during the test, and sudden force could not be applied. The test was conducted 3 times in total, and the best result was taken for statistical analysis.

5) The Standing on one-leg with eyes closed test (SOLECT)

The Standing on one-leg with eyes closed test evaluates the stability of the static posture by quantitative measurement, reflecting the balance ability of patients. The patient spread both hands, closed his eyes, and stood on one leg, with the other leg bent so that the angles between the two legs were 90 degrees. Time was recorded from the time when the foot left the ground, and the shaking stopped when the foot left the ground or stood up. The average of the three times was used for statistical analysis.

6) Bone mineral density test

The signals received by the scanning system after the double-energy DXA line penetrated the body were transmitted to the supporting software to calculate the average bone mineral density content (g/cm²) of the whole body, the left femur Ward triangle area, and the lumbar spine (L2~L4).

Secondary Outcome Measures:

1) Changes in the Short Form-36 (SF-36)

Changes from the Short Form-36 (SF-36) and European Quality of Life Five Dimension (EQ-5D-5L) scale at 0 months, 6 months, 12 months. The SF-36 score is used to evaluate an individual's health status and quality of life. The SF-36 score expressed as a number between 0 and 100, with higher numbers indicating better health. EQ-5D-5L evaluate quality of life from five aspects: action ability, self-care, daily activities, pain or discomfort, anxiety or depression. The score range generally ranges from less than 0 to 1, and the higher the score, the better the state; The VAS score range is 0-100, with higher scores indicating better health status.

2) Changes in the Hospital Anxiety and Depression Scale (HADS)

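### Bone density is a primary outcome, but the plan does not specify recording bone-active treatment or adjusting the comparison for its baseline use

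*Combined protocol and SAP*

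**What the plan says.** Section 1 opens by stating that "Chronic kidney disease bone mineral metabolism disorders exist in maintenance dialysis (MHD) patients". Section 2.1 puts bone density alongside physical fitness in the main objective. Item 6 under the primary outcome heading in section 2.4 takes from DXA the "average bone mineral density content (g/cm²) of the whole body, the left femur Ward triangle area, and the lumbar spine (L2~L4"). Section 2.2 sets the timing: "Measure the indicators of each group at baseline, months 6, 12".

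The design in section 2.2 is 50 patients "randomized into an intervention group of 25 cases and a control group of 25 cases", with no stratification factor named. The exercise arm is described as follows: "The intervention group undergo a 30 minute Baduanjin exercise under the guidance of a professional doctor before the dialysis day". The only statement about other care is "The intervention group practice three days a week, while the control group maintain routine treatment and daily activities", which has no counterpart for the intervention arm.

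The eligibility condition in section 2.3 that comes closest to background treatment is "Having received MHD treatment in this dialysis center for more than 3 months and maintaining stable condition". No eligibility criterion concerns drugs acting on bone, previous parathyroidectomy or mineral-metabolism laboratory values. Section 2.5 compares quantitative outcomes by t-test, or by a nonparametric test if the data are not normal, at P < 0.05 and with no covariate. Section 2.6 keeps case observation forms and refers to hospital source records, but does not list what the forms contain.

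**The concern.** Some routine treatment of mineral-bone disorder can be expected to act on bone density. Examples are vitamin D analogues, calcimimetics, phosphate binders, antiresorptives and parathyroidectomy. The documents give no figures on their use or effect, so that influence is an assumption here, but the plan's own opening sentence makes it foreseeable.

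Two separate things follow. First, baseline use is a likely predictor of bone density change. An unadjusted test leaves that predictable variation in the error term, in a trial with only 25 patients per arm. Second, treatment can start or stop during the 12 months, and randomisation does not prevent this from happening at different rates in the two arms. Section 3 removes a patient after surgery only if exercise cannot continue. A patient who has a parathyroidectomy and resumes exercise therefore stays in the comparison, and nothing in the plan calls for the event to be recorded. What is at stake is the precision of the bone density result and the ability to answer an obvious question about it.

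**Working it through.** **Inputs from the plan.** 50 patients, 25 per arm (section 2.2); unadjusted test at P < 0.05 (section 2.5), taken as two-sided because sidedness is not stated; sessions three days a week in one arm (section 2.2). The plan gives no effect size, SD or power for the 50, so the sample size cannot be reproduced. As a benchmark, 25 per arm with 80% power detects 0.81 SD by t-test (0.79 SD by normal approximation).

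**Assumed inputs.** K = 10 or 20 users of bone-active treatment among the 50; a difference e of 5 or 8 percentage points in 12-month bone density change between users and non-users; residual SD of 4 percentage points.

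**Step 1: how often chance imbalance occurs.** The number of users in one arm is hypergeometric (50, K, 25).
- K = 10: P(split of 7:3 or worse) = 0.289.
- K = 20: P(split of 12:8 or worse) = 0.387.

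An excess of 4 users moves the arm difference by 4/25 × 5 = 0.8 to 4/25 × 8 = 1.3 percentage points in that particular trial.

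**Step 2: is that bias?** No. The split varies in both directions across randomisations, and the t-test's standard error includes the variation due to users. Simulating 25:25 randomisation with no exercise effect under these assumptions (20,000 trials per scenario) gave a type I error between 4.9% and 5.2%.

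**Step 3: what it costs.** With p = K/50, the variance due to baseline use is e²p(1 − p). Its share of the total is e²p(1 − p) / [4² + e²p(1 − p)].

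| Users K | e | e²p(1 − p) | Share of variance | SE unadjusted = √(total × 2/25) |
|---|---|---|---|---|
| 10 | 5 | 25 × 0.16 = 4.00 | 4.00/20.00 = 20% | 1.26 |
| 20 | 5 | 25 × 0.24 = 6.00 | 6.00/22.00 = 27% | 1.33 |
| 10 | 8 | 64 × 0.16 = 10.24 | 10.24/26.24 = 39% | 1.45 |
| 20 | 8 | 64 × 0.24 = 15.36 | 15.36/31.36 = 49% | 1.58 |

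Adjusted, the SE is about 4 × √(2/25) = 1.13 percentage points in every row, apart from a small loss for estimating the covariate. If e is zero the gain is zero, and a larger residual SD makes it smaller.

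**Step 4: changes after randomisation.** If use differs between arms by D and the treatment shifts bone density by an assumed number of SDs, the arm difference shifts by the product. The rejection rate with no exercise effect then follows from the noncentral t on 48 df, with noncentrality shift × √(25/2).

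| D | Treatment effect (SD) | Shift (SD) | Rejection rate |
|---|---|---|---|
| 10 points | 0.3 | 0.03 | 5.1% |
| 20 points | 0.5 | 0.10 | 6.4% |
| 30 points | 0.8 | 0.24 | 13.2% |
| 40 points | 1.0 | 0.40 | 28.3% |

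The last row is 0.40/0.81 = 49% of the detectable difference. Nothing in the documents says which row applies, or that any does.

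**Step 5: unequal contact.** Three sessions a week for 52 weeks is at most 3 × 52 = 156 doctor-guided sessions, with no equivalent for the control arm. This is an upper bound. The three-day sentence does not itself say that every session is guided, and the wording that places sessions relative to dialysis days is unclear.

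**The case against.** The strongest reply is that the trial is randomised and usual care continues, which is normal for an exercise trial. Chance differences in baseline drug use are ordinary sampling variation. That stands: a reader might infer from the 29% and 39% in step 1 that the test is biased, and step 2 shows that it is not.

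A reader might also infer that the doctor guiding the exercise will alter bone treatment in one arm. The documents do not support that. They do not say that this doctor prescribes or reviews mineral-bone treatment, and all patients attend the same dialysis centre. Moderate assumptions in step 4 raise the rejection rate only to 5.1% to 6.4%; the large figures need large assumed differences. Moreover, a treatment change brought about by the exercise would be part of the effect of assignment, which argues against adjusting for it.

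A third tempting reading is that the data are lost and the bone objective cannot be answered. That also goes too far. Section 2.6 retains case observation forms and points to hospital records, and the forms may already include medication. What the documents support is that no collection is specified, not that none will occur or that it cannot be recovered.

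None of this removes the gap. A likely predictor of a primary outcome is neither specified for recording nor used in the analysis.

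**Conclusion.** The concern holds in a limited form. The planned bone density test is valid, and the loss from ignoring baseline treatment is one of precision: about 20% to 49% of the outcome variance for 10 to 20 users, a 5 to 8 point difference and a 4 point residual SD. All three inputs are assumptions, and the gain disappears if baseline use does not predict bone density change. Differential treatment change after randomisation is a plausible risk, ranging from negligible to about half the detectable difference under the assumptions tried. The documents do not establish it, and the dataset as specified could neither confirm nor exclude it.

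**What to change.** 1. In sections 2.4 and 2.5, specify that bone-active drugs and parathyroidectomy are abstracted from existing charts at months 0, 6 and 12, in the same way in both arms.
2. Prespecify that the bone density comparison at each site is adjusted for baseline use as one yes/no covariate, for example in a linear model replacing the plain t-test. Fix a narrow definition, with the treatments named, before outcome data are seen. Pooling drug classes with different effects would weaken the covariate.
3. Keep all bone density values in the main analysis and do not adjust it for changes made after randomisation.
4. Report starts, stops and parathyroidectomies by arm, so that a reader can judge whether background treatment diverged.

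An analysis that sets aside values after a treatment change conditions on events after randomisation and can introduce bias of its own. It should be omitted or labelled exploratory. No rule on who may change treatment is needed.

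The cost is chart abstraction for 50 patients at three time points and one covariate, with no extra tests, visits or patients.
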